- Independence of residuals (Durbin-Watson test)

- Absence of multicollinearity (Variance Inflation Factor < 5)
- Normality of residuals (Shapiro-Wilk on residuals)

Reported: Adjusted MD (β coefficient) with 95% CI, R^2 , adjusted R^2 , F-statistic, overall model p-value

SAP-4.3 CSD Prevalence — Analysis

Unadjusted:

- Chi-square test or Fisher's exact test (if expected cell count < 5)
- Relative Risk (RR) with 95% CI
- Absolute Risk Reduction (ARR) and Number Needed to Treat/Harm (NNT/NNH)

Adjusted:

- **Binary logistic regression** at 6–8 weeks and at 6–7 months
- Covariates: same set as RMT regression model
- Variables with $p < 0.20$ in univariate analysis AND a priori confounders (age, parity, BMI, indication) included
- Model fit: **Hosmer-Lemeshow test**
- Multicollinearity: **Variance Inflation Factors (VIF)**
- Discrimination: **Area Under the ROC Curve (AUC)**
- Results expressed as adjusted **Odds Ratios (OR)** with 95% CI

SAP-5. SECONDARY OUTCOME ANALYSES

SAP-5.1 Continuous Secondary Outcomes

- Unadjusted: t-test or Mann-Whitney U as appropriate
- Adjusted: Multiple linear regression (same covariate set)
- Results: Mean difference or median difference with 95% CI

SAP-5.2 Binary Secondary Outcomes (Complications, Transfusion)

- Unadjusted: Chi-square or Fisher's exact test
- Results: RR, ARR, NNT/NNH with 95% CI

SAP-5.3 CSD Morphological Dimensions

Analyzed within the **CSD-positive subgroup only**:

- Depth, length, width: Mann-Whitney U test
- **CSD Volume** (ellipsoid formula): Mann-Whitney U test

SAP-5.4 Repeated Measures — RMT at 6 Weeks and 6 Months

Method: Linear Mixed-Effects Model (LME)

Model structure:

- Fixed effects: treatment group, time point (6 weeks vs. 6 months), treatment × time interaction
- Random effect: participant-level intercept (accounts for within-subject correlation)
- Covariance structure: Unstructured (preferred); compound symmetry if convergence issues

Interpretation:

- Significant interaction ($p < 0.05$): treatment effect differs across time points
- Non-significant interaction: main effects interpreted independently

SAP-5.5 Symptom Outcomes (Ordinal / Binary)

- Binary symptoms (spotting, dyspareunia): Chi-square or Fisher's exact test; RR with 95% CI
- **Paired temporal evolution** (6 weeks → 6 months within each group): **McNemar's test**
- Adjusted: Binary logistic regression

SAP-5.6 Hemoglobin Variation and Blood Loss

- ΔHb : t-test or Mann-Whitney U; mean difference with 95% CI

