- PSTEV and PSTC: Mann-Whitney U (likely non-normal); median difference with 95% CI

SAP-6. ADVANCED ANALYTICAL METHODS

SAP-6.1 Clinical Predictive Model for CSD

A **clinical predictive model** for CSD formation will be developed using **Firth penalized logistic regression**, justified by the ratio of events to variables approaching the threshold defined by Peduzzi et al.

Model development:

- Variable selection: univariate screening ($p < 0.20$) + a priori clinical variables
- Stability: **Bootstrap validation (10,000 replications)**
- Optimal threshold: **Youden Index**
- Internal validation: **10-fold cross-validation** and **70/30 data partition**
- Performance: AUC, sensitivity, specificity, positive and negative predictive values

SAP-6.2 Mediation Analysis

The **mediating role of CSD at 6 weeks** on the relationship between hysterorrhaphy technique and RMT at 6 months will be assessed using the **counterfactual mediation framework (Imai et al.)**.

Estimated quantities:

- **ACME** (Average Causal Mediation Effect): indirect effect through CSD at 6 weeks
- **ADE** (Average Direct Effect): direct effect of technique on RMT
- **Total Effect** and **proportion mediated**

Method: Bootstrap with **10,000 replications**

Sensitivity analysis: Critical ρ (rho) analysis to quantify robustness to unmeasured confounders

SAP-6.3 Inter-Operator Homogeneity

Breslow-Day test for homogeneity of treatment effects across operators (surgeons), to assess whether results are consistent regardless of the individual performing the procedure.

SAP-6.4 Measurement Reproducibility

Inter-observer concordance will be evaluated by **double-blind reading (n = 30 randomly selected examinations)**:

- Continuous variables (RMT, AMT): **Intraclass Correlation Coefficient (ICC)**
- Categorical variables (CSD presence): **Cohen's Kappa**

Temporal concordance of RMT measurements (6 weeks vs. 6 months):

- **Lin's Concordance Correlation Coefficient**
- **Bland-Altman analysis** (mean difference and limits of agreement)

SAP-7. SUBGROUP ANALYSES

Pre-specified subgroup analyses for the primary outcome (RMT at 6–7 months):

Subgroup Factor	Categories	Statistical Test
BMI category	< 30 vs. 30–34.9 kg/m ²	Interaction term in regression
Gestational age	37–38+6 vs. ≥ 39 weeks	Interaction term
Indication for CS	Labor dystocia vs. Fetal indication vs. Maternal indication	Interaction term
Uterine exteriorization	Yes vs. No	Interaction term

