6.2 CSD Prevalence Analysis

Unadjusted: Chi-square or Fisher's exact test → RR, ARR, NNT/NNH with 95% CI

Adjusted: Binary logistic regression at 6–8 weeks and 6–7 months

- Variables: $p < 0.20$ in univariate + a priori confounders
- Fit: Hosmer-Lemeshow test
- Multicollinearity: VIF
- Discrimination: AUC (ROC curve)
- Results: Adjusted OR with 95% CI

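### The adjusted CSD and symptom models use ordinary logistic regression with no rule for sparse events, although SAP-6.1 adopts Firth for CSD on events-per-variable grounds: a modest, cheap improvement, not an invalidating error

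*SAP*

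**What the plan says.** - **Adjusted CSD effect.** SAP-4.3 specifies "Binary logistic regression at 6–8 weeks and at 6–7 months". Section 6.2 of the combined document agrees: "Adjusted: Binary logistic regression at 6–8 weeks and 6–7 months". Neither names a penalized or exact method, or a fallback.
- **Size of the CSD model.** SAP-4.3 gives two rules: "Covariates: same set as RMT regression model" and "Variables with $p < 0.20$ in univariate analysis AND a priori confounders (age, parity, BMI, indication) included". Section 6.2 gives only the screening rule.
- **Adjusted symptom effects.** SAP-5.5 names binary logistic regression and gives no covariate list. The combined document has no adjusted symptom model.
- **CSD prediction model.** SAP-6.1 uses Firth penalization, "justified by the ratio of events to variables approaching the threshold". Section 8.1 of the combined document gives the same reason. Predictors are chosen by the same kind of rule as in SAP-4.3: a univariate screen at 0.20 plus a priori variables.
- **Unadjusted effects.** CSD and symptoms also have a chi-square or Fisher test with a relative risk. CSD adds absolute risk reduction and NNT.

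**The concern.** Events per variable depend on the data and the number of coefficients, not on whether a model is called predictive or is used to estimate a treatment effect. The plan judges events scarce enough to need a correction in one CSD model. It does not apply that correction to the model giving the adjusted treatment effect on the same outcome, nor to the symptoms, where events may be fewer. With few events per coefficient, ML pushes log odds ratios away from zero and makes them noisier, and under separation it has no finite solution. If a symptom model separated, the analyst would have to choose a remedy after seeing the data, which the SAP says it exists to prevent.

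**Working it through.** **1. The plan's own figure.** Protocol section 11, for RMT: n = 2 × (1.96 + 0.842)² × 3.5² / 1.3² = 113.8, so 114 per group; 114 / 0.70 = 162.9, so 163. Both reproduce. (The 192 per group enrolled does not follow from 163, but nothing here depends on that.) No CSD rate, symptom rate or event count is given, so the rates below are assumptions.

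**2. Evaluable women.** 384 × (1 − 0.30) = 268.8; 268 is used, 134 per arm. SAP-10 analyses binary outcomes as complete cases, so losses reduce the events available.

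**3. Number of coefficients.**
- Upper end: treatment, age, BMI, gestational age, exteriorization, surgeon level and labor duration (7), plus indication (2), plus parity (1) = 10.
- Lower end, if the screen adds nothing: treatment, age, parity, BMI (4), plus indication (2) = 6.

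Indication is taken at the three levels in SAP-7: "Labor dystocia vs. Fetal indication vs. Maternal indication".

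**4. Events per variable (EPV).** True OR 0.50 (assumed). With reference-arm rate p and odds o = p/(1 − p), the other arm's rate is 0.5o/(1 + 0.5o). Events = 134 × the sum of the two rates.

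| Reference-arm rate | Other arm | Events | EPV, 10 coef. | EPV, 6 coef. |
|---|---|---|---|---|
| 50% | 33.3% | 112 | 11 | 19 |
| 40% | 25.0% | 87 | 9 | 15 |
| 30% | 17.6% | 64 | 6 | 11 |
| 20% | 11.1% | 42 | 4 | 7 |
| 10% | 5.3% | 20 | 2 | – |
| 5% | 2.6% | 10 | 1 | – |

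The documents do not state the threshold value. If it is 10, the 10-coefficient model needs about 100 CSD cases, or 100/268 = 37% overall.

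**5. Simulation for CSD, ML against Firth.** Covariate effects are assumed.
- 10 coefficients, 3,000 trials per rate: mean ML log OR −0.740, −0.727, −0.732 and −0.729 at 20, 30, 40 and 50%, against a true −0.693. That is 7%, 5%, 6% and 5% too large. Firth gave −0.690 to −0.699. MSE ratios (Firth/ML) were 0.86, 0.88, 0.89 and 0.90.
- Repeat runs with other covariate effects put the ML bias mostly at 4–9%, and the MSE reduction at 10–15%.
- 6 coefficients: bias about 1–5%, MSE reduction 7–9%.
- On the OR scale, at overall rates of 20–37% with 269 women, ML averaged 0.48 for a true 0.50; ln 0.48 = −0.734, which is 6% beyond −0.693.
- ML coverage was 94–97%. ML type I error was 5–6% at 20–30% prevalence and 4.9% at 37%. No CSD model failed at rates of 20% or more.

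**6. Symptoms.** Ten coefficients are assumed, because SAP-5.5 lists none.
- 10% reference rate: ML bias 14–15%, MSE about 25% lower with Firth, about 1% of ML fits failing.
- About 5%: ML failed in roughly 10–20% of trials. In the rest, Firth lowered MSE by 37–38%.

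**7. Which coefficient fails.** The treatment OR has no finite ML estimate essentially only when an arm has zero events. At a 5% reference rate: 0.95^134 = 0.001 and 0.974^134 ≈ 0.03, so about 3%. At a 5% overall rate (6.6% and 3.4%) it is about 1%. The other failures come from covariates.

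**The case against.** The strongest case for the plan as written has four parts.

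- **SAP-6.1 is a different fitting task.** It adds a 70/30 partition, 10-fold cross-validation and 10,000 bootstrap replications, so many fits see fewer events and can separate when the full data do not. It states no variable count, so its remark need not carry over exactly to SAP-4.3. This stands in part: the mismatch is an unexplained difference rather than a proven contradiction. But the reason SAP-6.1 gives is events per variable, not resampling, and it concerns the same outcome and the same kind of variable selection.
- **Ten coefficients is the upper end for CSD.** This stands, so results are given for 6 as well. Firth does not resolve the two covariate rules in SAP-4.3.
- **Other analyses give the treatment effect.** The unadjusted tests and relative risks do not depend on events per variable. SAP-4.2 labels the adjusted analysis primary for RMT; SAP-4.3 gives no such label for CSD. This stands, but the adjusted OR will still be reported.
- **The symptom case rests on assumed rates,** and SAP-9 calls secondary outcomes exploratory. This stands, so that part is conditional.

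A reader might infer that the treatment ORs are materially inflated or not estimable. The documents do not support that. For CSD the shift is about 0.50 to 0.48 with near-nominal coverage and no failures. For symptoms no rate is stated, and most failures at low rates are not in the treatment term. Nor does the SAP call the prediction model exploratory; it sits under advanced methods.

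**Conclusion.** The point holds as a modest improvement. The plan uses a small-sample correction for one CSD model and leaves it out, without explanation or fallback, of the adjusted treatment-effect models for CSD and symptoms.

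For CSD the cost is a log OR about 1–5% (6 coefficients) to 4–9% (10 coefficients) too large, with 7–15% of the MSE avoidable. That would not invalidate the CSD conclusion. For symptoms, real difficulty arises only at rates of about 5% or lower; there the main harm is an unplanned choice when a model fails.

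These sizes assume 30% loss, a true OR of 0.50, the stated range of event rates, 6–10 coefficients for CSD and 10 for symptoms.

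**What to change.** State in SAP-4.3, SAP-5.5 and section 6.2 of the combined document that adjusted binary treatment-effect models are fitted by Firth-penalized logistic regression with profile penalized-likelihood confidence intervals, as the method already adopted in SAP-6.1. Report ordinary ML as a sensitivity analysis for CSD. Make the change before unblinding; otherwise record it as a justified deviation, as SAP-1 requires.

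Cost: one sentence in each place, and running these models in R, which the plan already lists, rather than SPSS, to which it assigns primary analyses. Expect about 1–3 points less nominal power for CSD. The covariate list for SAP-4.3, and a list for SAP-5.5, still need to be settled separately.

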All randomized participants who underwent the surgical intervention (regardless of which technique was ultimately performed).

Protocol deviations will be prospectively classified as **major** (potentially affecting primary outcome validity) or **minor** (unlikely to affect outcomes) and documented in a deviation log.

SAP-3. BASELINE CHARACTERISTICS

Baseline characteristics will be summarized for the **ITT population** by treatment group:

Variable Type	Summary Statistic
Continuous, normally distributed	Mean ± Standard Deviation
Continuous, non-normal distribution	Median (Interquartile Range, IQR)
Categorical	n (%)

Normality of continuous variables will be assessed using both the **Kolmogorov-Smirnov test** and the **Shapiro-Wilk test**, complemented by visual inspection of Q-Q plots and histograms.

Variables to be summarized include: age, BMI at delivery, gestational age, parity, indication for cesarean section, type of anesthesia, skin incision type, uterine exteriorization status, pre-operative hemoglobin and hematocrit, and attending surgeon (anonymized).

No inferential statistics (p-values) will be calculated for baseline comparisons, as any imbalances in a randomized trial result from chance rather than systematic bias (CONSORT Statement 2010).

SAP-4. PRIMARY OUTCOME ANALYSIS

Outcomes:

1. **RMT** at 6–8 weeks and 6–7 months (continuous, mm)
2. **CSD prevalence** at 6–8 weeks and 6–7 months (binary)

SAP-4.1 RMT — Unadjusted Analysis

- **If normally distributed:** Independent samples **t-test** (or Welch's t-test if unequal variances)
- **If non-normally distributed: Mann-Whitney U test**

Reported statistics:

- Mean \pm SD (or Median [IQR]) per group
- Mean difference (MD) with 95% Confidence Interval
- Two-sided p-value (significance threshold: $\alpha = 0.05$)
- Effect size: Cohen's d (t-test) or rank-biserial correlation (Mann-Whitney)

SAP-4.2 RMT — Adjusted Analysis (Primary)

A **multiple linear regression model** will be constructed:

Dependent variable: RMT at 6–7 months

Independent variables:

- Treatment group (primary predictor)
- Age (continuous)
- BMI (continuous)
- Gestational age (continuous)
- Uterine exteriorization (yes/no)
- Surgeon experience level (senior/resident Year 4–5)
- Duration of labor before cesarean section (if applicable)
- Indication for cesarean section

Model assumptions verified:

- Linearity (partial regression plots)
- Homoscedasticity (Breusch-Pagan test)

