6. PRIMARY OUTCOME STATISTICAL ANALYSIS

6.1 RMT Analysis

Step 1 — Unadjusted:

If normally distributed	Independent t-test (or Welch's t-test)
If non-normal	Mann-Whitney U test

Step 2 — Adjusted (primary analytical approach):

Multiple linear regression with RMT as dependent variable

Covariates: Treatment group, age, BMI, gestational age, uterine exteriorization, surgeon category, labor duration, CS indication

Reported: Adjusted MD, 95% CI, R^2 , adjusted R^2 , F-statistic, model p-value

Assumption verification: Linearity, homoscedasticity (Breusch-Pagan), independence (Durbin-Watson), multicollinearity ($VIF < 5$), normality of residuals (Shapiro-Wilk)

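### The adjusted model for cesarean scar defect has two covariate rules that do not match, one of them a p < 0.20 screen on outcome data, and neither document names the primary analysis for this co-primary endpoint

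*SAP*

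**What the plan says.** CSD prevalence is a co-primary endpoint at 6–8 weeks and 6–7 months (combined document's SAP, section 3). SAP-9 gives each co-primary endpoint a two-sided 0.05.

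SAP-4.3 plans an unadjusted comparison, reported as risk ratio, absolute risk reduction and NNT/NNH, and a logistic regression at each visit, reported as an odds ratio. Two consecutive bullets set the covariates of that regression:

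- "Covariates: same set as RMT regression model"
- variables with p < 0.20 "in univariate analysis AND a priori confounders (age, parity, BMI, indication) included"

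The list that the first bullet points to is in SAP-4.2: age, BMI, gestational age, "Uterine exteriorization (yes/no"), "Surgeon experience level (senior/resident Year 4–5"), "Duration of labor before cesarean section (if applicable") and indication, besides treatment group.

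Section 6.2 of the combined document's SAP has only the second rule, p < 0.20 "in univariate + a priori confounders", and does not say which confounders these are.

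For RMT, both documents name the primary analysis. One heading begins "SAP-4.2 RMT — Adjusted Analysis (Primary", the other "Step 2 — Adjusted (primary analytical approach". The CSD sections carry no such label.

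**The concern.** SAP-1 says that the plan exists to limit analytical decisions made after the fact. For CSD it leaves two open.

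The first is the covariate set. In a randomized trial, adjustment covariates are best fixed beforehand for their prognostic value. A univariate screen against CSD lets the outcome data choose the model, separately at each visit, and the reported interval takes no account of that choice. SAP-3 declines baseline p-values because imbalances arise by chance, so a p-value screen for confounders sits oddly in the same plan.

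The second is the result itself. An unadjusted risk ratio and an adjusted odds ratio stand side by side, on different scales, with neither named as the one that decides the endpoint. If they fall on opposite sides of 0.05, the plan does not say which counts. The principal investigator is unblinded (protocol section 7.3), so this should not be left until results are seen.

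**Working it through.** **1. The plan's own figures.** The only computed design figures concern RMT (protocol section 11). 2 × (1.96 + 0.842)² × 3.5² / 1.3² = 113.8, so 114 per group, and 114 / 0.70 = 162.9, so 163. Both reproduce. There is no design figure for CSD, and no CSD prevalence is given.

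**2. The two rules of SAP-4.3 side by side.**

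| Variable | Rule 1: SAP-4.2 list | Rule 2: screen plus a priori |
|---|---|---|
| Age, BMI, indication | in | in |
| Parity | not listed | in |
| Gestational age, exteriorization, surgeon level, labor duration | in | only if p < 0.20 |
| Any other recorded variable | not listed | unclear; no candidate pool stated |

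Treating the SAP-4.2 list as the pool to be screened does not reconcile the rules, because parity is not in it.

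**3. How far the screen can move the model.** Assume that it covers only the four variables in the third row.

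- Possible models per visit: 2⁴ = 16.
- If all four are independent and unrelated to CSD, the chance that at least one enters at a given visit is 1 − 0.8⁴ = 0.59.
- The chance that the two visits end with different sets is another quantity. With uncorrelated screening statistics across visits it is 1 − (0.8² + 0.2²)⁴ = 1 − 0.68⁴ = 0.79. The same women are examined twice, so positive correlation is likely. At correlations of 0.5, 0.7, 0.8 and 0.9 the chance is 0.71, 0.62, 0.54 and 0.41. The documents do not give the correlation.

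**4. Effect on the treatment comparison.** Three analyses were simulated with no treatment effect: unadjusted chi-square, logistic regression under rule 1, and logistic regression under rule 2. The assumptions were:

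- 134 per group (192 × 0.70 = 134.4).
- CSD prevalence about 25% or 50%.
- Log-odds effects of 0, 0.2 or 0.4 per SD for BMI, gestational age and labor duration, and twice that between the two levels of exteriorization and surgeon level; no effect for the rest.
- 1,500 runs per scenario. The simulation standard error at 5% is √(0.05 × 0.95 / 1,500) = 0.6 percentage points.

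| Quantity, one visit | Range over six scenarios |
|---|---|
| Rejection rate of each analysis alone | 4.1% to 6.0% |
| At least one of the three rejects | 5.7% to 7.4% |
| The three disagree on significance | 2.2% to 4.4% |
| Odds ratio under rule 1 divided by rule 2, central 95% of runs | about 0.94 to 1.06 |
| Different covariate sets selected | 11 to 16 |

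**5. Scale.** With assumed prevalences of 40% and 30%, the risk ratio is 0.75 and the odds ratio is (0.30/0.70) / (0.40/0.60) = 0.64. With 60% and 45%, they are 0.75 and (0.45/0.55) / (0.60/0.40) = 0.55. The same data look stronger on the odds ratio scale, so the effect measure needs naming along with the analysis.

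**The case against.** The bullets in SAP-4.3 can be read as a union: the full RMT set, plus parity, plus anything else that passes the screen. Then gestational age, exteriorization, surgeon level and labor duration are always in, and the rules are not strictly incompatible. That reading is possible, so the text is better called unreconciled than impossible. It still leaves a screen with no stated candidate pool, and it is not available in section 6.2 of the combined document, which lacks the first rule. The precedence clause in section 1 of that SAP ranks it over the protocol and does not mention the standalone SAP.

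The second objection is that little changes in practice. Randomization makes covariates independent of treatment on average, so each analysis keeps close to its nominal error and the odds ratio barely moves. This stands, and it limits the weight of the point. It does not justify the screen, which adds a data-driven choice without a stated benefit.

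The third is that an odds ratio beside a risk ratio is a reporting matter, since both are labelled. This also stands. Converting to one scale is a preference; saying which measure is primary is not.

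**Conclusion.** The point holds as a failure of pre-specification for a co-primary endpoint. The covariate rules need reconciling, the p < 0.20 screen should go, and the primary CSD analysis is not named. It should be fixed, but it does not threaten the trial's validity.

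Three stronger conclusions might be inferred, and the documents do not support them.

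- That the headline CSD result is data-dependent. The unadjusted test, risk ratio and absolute risk reduction involve no covariate selection. What depends on the data is the screened odds ratio; what is open is which result is the headline.
- That the models at the two visits will usually differ. The 59% concerns one visit. The chance of a difference runs from 79% down to 41% as the assumed correlation rises from 0 to 0.9.
- That type I error is seriously inflated. Free choice among the three analyses raises it from 5% to roughly 6–7% at one visit.

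These sizes rest on assumed prevalences and covariate effects and on a screen limited to four variables. A wider candidate pool, which section 6.2 does not exclude, was not simulated.

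**What to change.** - Delete the p < 0.20 screen from SAP-4.3 and from section 6.2 of the combined document's SAP. It may stay in the exploratory predictive model of SAP-6.1.
- State one fixed covariate list for both visits, identical in both documents: age, BMI, gestational age, exteriorization, surgeon level, labor duration and indication, plus parity if it is kept as an a priori confounder. State how each is coded, including labor duration when there was no labor.
- Name one CSD analysis and one effect measure as primary, for example the adjusted model to match RMT, with the other as supportive.
- Optionally, report a standardized risk ratio and risk difference from the adjusted model, to match the planned unadjusted measures.
- Date the change and record it before unblinded results are seen.

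The cost is SAP wording. Parity is already among the baseline variables in SAP-3, and a fixed-list logistic model runs in SPSS, the package named for primary analyses. Only the optional standardization would need some additional programming, for which R is already planned.

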Type of cesarean section	Scheduled vs. Intrapartum	Interaction term
Surgeon category	Senior vs. Resident Year 4–5	Interaction term

Test for interaction: Likelihood ratio test comparing models with and without the interaction term.

All subgroup analyses are exploratory and hypothesis-generating. No correction for multiple comparisons is applied to subgroup analyses; results will not drive primary conclusions.

Results will be presented in **forest plots**.

SAP-8. SENSITIVITY ANALYSES

Analysis	Method
SA-1: Per-Protocol population	Repeat primary analysis in PP population
SA-2: Intraoperative complication exclusion	Exclude participants with major intraoperative events (corporeal hysterotomy, hysterotomy extension > 2 cm)
SA-3: Multiple imputation for missing RMT	MICE — 5 scenarios: observed data, LOCF, best case, worst case, 6-week status carry-forward
SA-4: Inverse Probability Weighting (IPW)	Adjust for informative loss to follow-up
SA-5: Binary threshold analysis	Proportion with RMT < 2.5 mm and RMT < 3.0 mm; Chi-square test
SA-6: Complete case analysis	For comparison with imputed results

SAP-9. MULTIPLICITY AND TYPE I ERROR CONTROL

- **Primary outcomes:** $\alpha = 0.05$, two-sided, for each co-primary endpoint (RMT and CSD prevalence at 6 weeks and 6 months)
- **Secondary outcomes:** Exploratory; **Holm-Bonferroni correction** applied to control family-wise error rate
- **Unmeasured confounders:** **E-value** calculated to quantify the minimum strength of an unmeasured confounder needed to explain away observed associations

SAP-10. MISSING DATA STRATEGY

Data Type	Strategy
Primary outcome (RMT at 6 months)	Five imputation scenarios (MICE)
Secondary continuous outcomes	Complete case + sensitivity with imputation if > 10% missing
Binary outcomes	Complete case analysis

Symptom questionnaires	Linear mixed model (full information maximum likelihood)
------------------------	--

Missing data mechanism assessed by **Little's MCAR test**.

Participants lost to follow-up compared to completers on key baseline variables; reasons for dropout documented and reported.

SAP-11. PRESENTATION OF RESULTS

Results reported in accordance with **CONSORT 2010** guidelines:

- **Table 1:** Baseline characteristics (ITT population) — no p-values
- **Figure 1:** CONSORT flow diagram
- **Table 2:** Primary and secondary outcomes with between-group comparisons
- **Table 3:** Subgroup analysis (forest plots)
- **Table 4:** Multivariate analysis results

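### The CSD co-primary changes from relative and absolute risk to an odds ratio at the adjustment step, so no covariate-adjusted absolute effect is planned

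*SAP*

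**What the plan says.** SAP-9 of the standalone SAP tests at two-sided 0.05 "for each co-primary endpoint (RMT and CSD prevalence at 6 weeks and 6 months", so CSD at each visit is a primary comparison.

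- **Unadjusted (SAP-4.3):** "Relative Risk (RR) with 95% CI", and "Absolute Risk Reduction (ARR) and Number Needed to Treat/Harm (NNT/NNH".
- **Adjusted (SAP-4.3):** "Binary logistic regression at 6–8 weeks and at 6–7 months", with "Results expressed as adjusted Odds Ratios (OR) with 95% CI".
- **Combined document, SAP section 6.2:** unadjusted "RR, ARR, NNT/NNH with 95% CI"; adjusted "Results: Adjusted OR with 95% CI".

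Neither text plans an adjusted relative risk, an adjusted risk difference, standardisation, or a log-binomial or Poisson model for CSD. The mediation analysis has RMT as its outcome, and the inverse probability weighting addresses loss to follow-up, so neither fills the gap.

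Only RMT has an adjusted analysis marked as the main one ("SAP-4.2 RMT — Adjusted Analysis (Primary"). For CSD, neither text says which measure carries the conclusion.

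**The concern.** RMT stays on one scale: a mean difference before adjustment and an adjusted mean difference after. A reader can see what adjustment did. For CSD, a move from relative risk to odds ratio mixes the effect of adjustment with a change of scale. When there is an effect and CSD is common, the odds ratio lies further from 1 than the relative risk for the same two risks, so adjustment could appear to strengthen the result when only the measure changed.

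Three things are at stake:

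- The absolute effect, which surgeons would act on, exists only in unadjusted form.
- With no CSD measure named as primary, either one could be put forward after the data are seen.
- The planned E-value (SAP-9; section 11 of the combined document's SAP) is defined on the risk-ratio scale, and the plan does not say which CSD estimate would enter it.

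**Working it through.** **Figures in the plan.** No CSD rate is given. The only sample size is for RMT at 6 months (protocol section 11) and it reproduces: 2 × (1.96 + 0.842)² × 3.5² / 1.3² = 113.8, so 114 per group, and 114 / 0.70 = 163. It does not involve CSD. With 192 enrolled per group and 30% loss, 192 × 0.70 ≈ 134 per group would be evaluable.

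**Step 1: scale alone.** With p0 the reference risk and p1 the comparison risk, RR = p1/p0 and OR = [p1/(1−p1)] / [p0/(1−p0)]. Holding RR at 0.667 (assumed; a true relative reduction of 33%):

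| Reference risk (assumed) | OR | Reduction if the OR is read as an RR |
|---|---|---|
| 5% | 0.655 | 34% |
| 10% | 0.643 | 36% |
| 30% | 0.583 | 42% |
| 50% | 0.500 | 50% |
| 60% | 0.444 | 56% |

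**Step 2: from an adjusted OR to risks.** Assume a logistic model with conditional OR 0.50 and a normally distributed covariate score Z with SD 0.55. Choose the intercept a so that the mean of expit(a + Z) equals the reference risk. The standardised comparison risk is the mean of expit(a + ln 0.50 + Z).

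| Reference risk | Comparison risk | RR | Risk difference (points) | NNT | Marginal OR |
|---|---|---|---|---|---|
| 10% | 5.3% | 0.53 | 4.7 | 21.5 | 0.51 |
| 20% | 11.4% | 0.57 | 8.6 | 11.6 | 0.51 |
| 30% | 18.2% | 0.61 | 11.8 | 8.4 | 0.52 |
| 40% | 25.8% | 0.64 | 14.2 | 7.0 | 0.52 |
| 50% | 34.3% | 0.69 | 15.7 | 6.4 | 0.52 |
| 60% | 44.0% | 0.73 | 16.0 | 6.2 | 0.52 |

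One adjusted OR of 0.50 fits NNTs from about 6 to 21, so it does not determine the adjusted absolute effect. Over 20–60% it stands beside a true relative reduction of 43% down to 27%.

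**Step 3: what drives the gap.** The marginal OR of 0.51–0.52 is close to the conditional 0.50, so non-collapsibility contributes little. It reaches 0.61 only if the covariate-score SD is taken as high as 1.5. In a simulation of 268 evaluable women (2 × 134), the standardised risk difference had variance 0–5% below the unadjusted one. Precision is therefore not the argument.

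**Step 4: E-value.** The formula is 1/RR + √[(1/RR) × (1/RR − 1)]. Entering 0.50 as if it were an RR gives 2 + √2 = 3.4. The matching RR of 0.64 (40% reference risk) gives 1.5625 + √(1.5625 × 0.5625) = 2.5.

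**Step 5: non-ignorable loss, illustration only.** Both SAPs analyse binary outcomes on complete cases. Take the 40% row with 30% lost in each arm. Let the log-odds of loss in the reference arm rise by 1 per SD of Z, and let loss in the other arm be unrelated to Z. The observed risks become 36.8% and 25.8%, a difference of 11.0 points against a true 14.2. Standardising over the analysed women gives 38.4% − 24.5% = 13.9. This mechanism is assumed, and the correction works only because Z is in the model.

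**The case against.** A labelled adjusted odds ratio beside an unadjusted relative risk, risk reduction and NNT is a legitimate analysis. Several stronger readings are tempting, and the documents do not support them.

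- **That the absolute effect is missing or the CSD comparison is invalid.** Both SAPs plan the unadjusted RR, ARR and NNT/NNH, and 1:1 randomisation makes them valid when loss is ignorable. Only the adjusted absolute effect is absent.
- **That the odds ratio will be headlined and will overstate the benefit.** Neither text gives it that role. SAP-11 tabulates between-group comparisons and multivariate results separately. Overstatement needs a reader to take a labelled odds ratio for a relative risk.
- **That the two results cannot be compared.** A crude odds ratio follows from the same two-by-two table and could be set beside the adjusted one. That cures the mismatch of scale, though it gives no adjusted absolute effect.
- **That the gap is certainly large.** Prevalence is not stated, and at 5–10% the gap is negligible. SAP-6.1 justifies Firth regression by the ratio of events to variables, which hints that events may be limited.
- **That symptoms share the defect.** SAP-5.5 names logistic regression for the adjusted analysis but states no effect measure, so an odds-ratio-only report is not documented there.

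Two cautions about the remedy also stand. An NNT interval is unbounded or discontinuous when the risk-difference interval reaches zero. In the 20% row with 134 per arm, SE = √(0.20 × 0.80/134 + 0.114 × 0.886/134) = 0.044, so the 95% CI runs from about 0 to 17 points. And standardisation does not define the estimate until the covariates are fixed. SAP-4.3 gives two rules: the RMT set, and screening at p < 0.20 plus named confounders that include parity, which is not in the RMT set.

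What remains is the change of measure at the adjustment step, the lack of an adjusted absolute effect, and silence on which CSD measure is primary.

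**Conclusion.** The point holds as an estimand and reporting weakness in a co-primary endpoint, present in both SAP texts. It does not bias or invalidate the planned unadjusted comparison.

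Its size is conditional. For a conditional OR of 0.50 and covariate-score SD of 0.55, the corresponding RR is about 0.53 at 10% reference risk, 0.61 at 30% and 0.69 at 50%. The OR, the covariate SD and the prevalences are all assumptions. The direction (OR further from 1 than RR for the same two risks, when there is an effect) does not depend on them. Non-collapsibility and precision are minor. Any protection against covariate-related loss is a possible further benefit whose size the documents cannot settle. The change is worth making because it is nearly free and puts the adjusted result on the scale the plan already uses.

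**What to change.** Amend SAP-4.3 and section 6.2 of the combined document's SAP in the same words, before database lock and unblinding:

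1. Fix one covariate set for the CSD logistic model, replacing the two rules in SAP-4.3 and the screening rule in section 6.2.
2. At each visit, average the predicted risks with every analysed woman set to SLC, then to DLC. Report the adjusted risk difference and adjusted RR with bootstrap or delta-method 95% CIs.
3. Keep the adjusted OR beside them, labelled as a conditional odds ratio.
4. Give NNT as a point value, with an interval only when the risk-difference CI excludes zero.
5. State which CSD measure carries the conclusion.
6. If an adjusted effect is used for the E-value, use the adjusted RR.

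**Cost:** SAP wording and a few lines of R; R and bootstrap methods are already planned. No new data, participants or visits are needed. The downside is a little more analysis work and reliance on the logistic model being adequate. The unadjusted RR and ARR stay in the report as a check on that.
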